6.1.2 Derived and Transformed Data

➤ Baseline

The last non-missing assessment on or before the first dose of vaccination will be defined as the baseline.

➤ Date Conversion

Month=days/30.4375, Year=days/365.25, rounding to 1 decimal place.

➤ Adverse Event

Occurrence time of AE (days) = Start date of AE - the corresponding vaccination date

AE duration(days) = End date of AE - Start date of AE + 1

➤ Treatment Emergent Adverse Event (TEAE)

TEAEs are defined as adverse events that occur after the first vaccination (including the day of the first vaccination) or worsen after vaccination. Programming is carried out according to the following rules:

- ❖ If the start date of adverse events is after (including simultaneously) the date of the first vaccination, they will be counted as TEAE.
- ❖ If the start date of adverse events is before the date of the first vaccination, they will be counted as non-TEAE.
- ❖ If the start date of adverse event or the date of the first vaccination is missing, making it impossible to determine whether the adverse event occurred after the first vaccination, then such adverse events shall all be counted as TEAE.

➤ Handling of incorrect vaccination

- ❖ In the immunogenicity evaluation, subjects will be analyzed according to the vaccine they were randomized to receive, in accordance with the Intention-To-Treat (ITT) principle.
- ❖ In the safety evaluation, subjects will be analyzed according to the vaccine they actually received, in accordance with the All Subjects as Treated (ASaT).

➤ Relationship of AEs

- ❖ Related to the study, vaccine means that the relationship between the adverse event and the study vaccine is "possibly related", "probably related", or "definitely related".

- ❖ Unrelated to the study vaccine means that the relationship between the adverse event and the study vaccine is "possibly unrelated" or "definitely unrelated".

➤ **Coding**

AEs, SAEs, and concomitant procedures will be encoded according to version 27.0 of the Medical Dictionary for Regulatory Activities (MedDRA). Concomitant medications/concomitant vaccines will be encoded according to the WHODD_2024-Mar-1 version of the World Health Organization Drug Dictionaries (WHODD).

➤ **Prior and Concomitant Medication**

The determination of prior and concomitant medication uses follows the following rules, respectively:

- ✓ Prior medication, medications with an end date that is before the first vaccination date.
- ✓ Concomitant medication, medications with a start date before the first vaccination date and an end date after any vaccination date, or with a start date after the first vaccination date.
- ✓ When it cannot be determined, the CRF collection shall prevail.

Prior and concomitant procedures determination rule is the same as that of prior and concomitant medications.

6.1.3 Visit Window

For by-visit summaries, data recorded at the nominal visit will be presented. That is, unscheduled measurements will not be included in by visit summaries but might contribute to the baseline timepoint and/or maximum value, where required.

6.1.4 Analysis Software

All analyses will be conducted using SAS version 9.4.

6.1.5 Table and Listing

➤ **Table**

Results will be generally summarized by groups (including test group 1, test group 2, control group 1, and control group 2). Groups are generally presented in the form of columns, and the specific group display will be adjusted according to the actual situation.

➤ **Listing**

Unless otherwise specified, all listings will include group, site, subject number, and the original data will be displayed first. The listing will be generally sorted in sequence by group, site, subject number, visit, or other relevant times (such as the start date of AE).

6.2 Disposition of Subjects

The number of subjects screened, enrolled, and completed the trial for each group, as well as the number of subjects entered into each analysis set, will be summarized separately, and the reasons for subjects who failed to be screened and the reasons for those who withdrew will be analyzed. The list of subjects who failed to be screened, the list of subjects who withdrew, and the list of subjects excluded from each analysis set will be presented separately. A flow chart of the trial will be provided.

6.3 Demographic and Baseline Characteristics

Descriptive statistics will be performed separately for the following demographic data and baseline characteristics, including age(in months), gender, ethnicity, body length/height, weight, and pre-vaccination axillary temperature.

Based on the distributional characteristics of the variables, ANOVA will be used to statistically compare between-group differences in age, body length/height, weight, and pre-vaccination axillary temperature. The Chi-square test or Fisher's exact test will be used to statistically compare between-group differences in gender and ethnicity. Demographic data and baseline characteristics will be listed. The previous severe medical history and current medical history will be encoded using MedDRA version 26.1 or higher. The number of subjects and incidence rates of previous severe medical history/current medical history will be calculated, respectively, according to the SOC and PT grades, and Fisher's exact test will be used to statistically test the differences in the frequency of previous severe medical history/current medical history between groups. All medical history will be listed.

The above analysis is based on mFAS, FAS, and PPS.

6.4 Compliance

Protocol deviations in each group will be summarized by total and classification. All protocol deviations will be listed.

Descriptive statistics of whether completed each vaccination, whether completed the immunogenicity blood collection will be presented for each group, and the Chi-square test /Fisher's exact test will be used to compare the differences between groups.

Compliance analysis will be based on all randomized subjects.

6.5 Concomitant Medications/Concomitant Vaccines/Concomitant Procedures

Concomitant medications will be encoded using the WHODD_2023-Mar-1 or higher version, and the number of subjects and rate of concomitant medications will be calculated by Anatomic Therapeutic Chemical (ATC) level 2 and Preferred Name (PN). Fisher's exact test will be used to test the differences between groups. Concomitant medications will be listed.

Concomitant vaccines will be encoded using the WHODD_2023-Mar-1 version, and the number of subjects and rate of concomitant vaccines will be summarized by ATC level 4 and preferred names. Fisher's exact test will be used to test the differences between groups. Concomitant vaccines will be listed.

Concomitant procedures will be encoded using the MedDRA 26.1 or higher version, and the number of subjects and rate of concomitant procedures will be calculated according to SOC and PT. Fisher's exact test will be used to test the differences between groups. Concomitant procedures will be listed. Above concomitant medications/concomitant vaccines/concomitant procedures will be analyzed based on SS, SS1, and SS2.

6.6 Analysis of Intercurrent Events

The intercurrent events of the primary estimand in each group will be summarized, and Fisher's exact

test will be used to compare the between-group differences. A list of intercurrent events will be presented.

The above intercurrent events will be analyzed based on all randomized subjects.

6.7 Study Hypothesis

❖ **Hypothesis test I:** For all subjects aged 6-35 months, 28d after completing of full-course vaccination, the SCR of serum HI antibody against influenza virus H1N1 and H3N2 subtypes in the test group is non-inferior to that in the pooled control group. That is:

$$\text{Null hypothesis } H_{10}: \pi_{iT} - \pi_{iC} < \Delta_1$$

$$\text{Alternative hypothesis } H_{1a}: \pi_{iT} - \pi_{iC} \geq \Delta_1$$

Where π_{iT} , π_{iC} represent the post-vaccination SCRs for serotype i ($i=1, 2$ corresponding to H1N1 and H3N2, respectively) in test group and combined control group. The non-inferiority margin is $\Delta_1 = -10\%$, and the significance level is one-sided $\alpha=0.025$.

❖ **Hypothesis test II:** For all subjects aged 6-35 months, 28d after completing of full-course vaccination, the GMT of serum HI antibody against influenza virus H1N1 and H3N2 subtypes in the test group is non-inferior to that in the pooled control group. That is:

$$\text{Null hypothesis } H_{20}: \frac{\text{GMT}_{iT}}{\text{GMT}_{iC}} < \Delta_2,$$

$$\text{Alternative hypothesis } H_{2a}: \frac{\text{GMT}_{iT}}{\text{GMT}_{iC}} \geq \Delta_2,$$

Where GMT_{iT} , GMT_{iC} represent the post-vaccination GMT for serotype i ($i=1, 2$ corresponding to H1N1 and H3N2, respectively) in test group and pooled control Group. The non-inferiority margin is $\Delta_2 = 2/3$, and the significance level is one-sided $\alpha=0.025$.

❖ **Hypothesis test III:** For all subjects aged 6-35 months, 28d after completing of full-course vaccination, the SCR of serum HI antibody against the influenza virus BV subtype in the test group is non-inferior to that in the combined control group. That is:

$$\text{Null hypothesis } H_{10}: \pi_{iT} - \pi_{iC} < \Delta_1,$$

$$\text{Alternative hypothesis } H_{1a}: \pi_{iT} - \pi_{iC} \geq \Delta_1,$$

Where π_{iT} , π_{iC} represent the post-vaccination SCRs for serotype i ($i=3$) in the test group and control group 1. The non-inferiority margin is $\Delta_1 = -10\%$, and the significance level is one-sided $\alpha=0.025$.

❖ **Hypothesis test IV:** For all subjects aged 6-35 months, 28d after completing of full-course vaccination, the GMT of serum HI antibody against influenza virus BV and BY subtypes in the test group is non-inferior to that in the control group 1. That is:

$$\text{Null hypothesis } H_{20}: \frac{\text{GMT}_{iT}}{\text{GMT}_{iC}} < \Delta_2,$$

$$\text{Alternative hypothesis } H_{2a}: \frac{\text{GMT}_{iT}}{\text{GMT}_{iC}} \geq \Delta_2,$$

Where GMT_{iT} , GMT_{iC} represent the post-vaccination GMT for serotype i ($i=3$) in the test group and control group 1. The non-inferiority margin is $\Delta_2 = 2/3$, and the significance level is one-sided $\alpha=0.025$.

❖ **Hypothesis test V:** For all subjects aged 6-35 months, 28d after completing of full-course

vaccination, the SCR of serum HI antibody against the influenza virus BY subtype in the test group is non-inferior to that in the control group 2. That is:

$$\text{Null hypothesis } H_{10}: \pi_{iT} - \pi_{iC} < \Delta_1,$$

$$\text{Alternative hypothesis } H_{1a}: \pi_{iT} - \pi_{iC} \geq \Delta_1,$$

Where π_{iT} , π_{iC} represent the post-vaccination SCRs for serotype i ($i=4$) in the test group and control group 2. The non-inferiority margin is $\Delta_1 = -10\%$, and the significance level is one-sided $\alpha = 0.025$.

❖ **Hypothesis test VI:** For all subjects aged 6-35 months, 28d after completing of full-course vaccination, the GMT of serum HI antibody against the influenza virus BY subtype in the test group is non-inferior to that in the control group 2. That is:

$$\text{Null hypothesis } H_{20}: \frac{\text{GMT}_{iT}}{\text{GMT}_{iC}} < \Delta_2,$$

$$\text{Alternative hypothesis } H_{2a}: \frac{\text{GMT}_{iT}}{\text{GMT}_{iC}} \geq \Delta_2,$$

Where GMT_{iT} , GMT_{iC} represent the post-vaccination GMT for serotype i ($i=4$) in the test group and control group 2. The non-inferiority margin is $\Delta_2 = 2/3$, and the significance level is one-sided $\alpha = 0.025$.

❖ **Hypothesis test VII:** For all subjects aged 6-35 months, 28d after completing of full-course vaccination, the lower limit of the 95% CI for the SCR of serum HI antibody against influenza virus H1N1, H3N2, BV, and BY subtypes in the test group is $\geq 30\%$. That is:

$$\text{Null hypothesis } H_{30}: \pi_{iT} < \pi_1,$$

$$\text{Alternative hypothesis } H_{3a}: \pi_{iT} \geq \pi_1$$

Where π_{iT} represents the post-vaccination SCR for serotype i ($i=1, 2, 3, 4$ corresponding to H1N1, H3N2, BV, and BY, respectively) in the test group, $\pi_1 = 30\%$, and the significance level is one-sided $\alpha = 0.025$.

❖ **Hypothesis test VIII:** For all subjects aged 6-35 months, 28d after completing of full-course vaccination, the lower limit of the 95% CI for the SPR of serum HI antibody against influenza virus H1N1, H3N2, BV, and BY subtypes in the test group is $\geq 60\%$. That is:

$$\text{Null hypothesis } H_{40}: \pi_{iT} < \pi_2,$$

$$\text{Alternative hypothesis } H_{4a}: \pi_{iT} \geq \pi_2$$

Where π_{iT} represents the post-vaccination SPR for serotype i ($i=5, 6, 7, 8$ corresponding to H1N1, H3N2, BV, and BY, respectively) in the test group, $\pi_2 = 60\%$, and the significance level is one-sided $\alpha = 0.025$.

6.8 Immunogenicity Evaluation

Immunogenicity analysis will be based on mFAS, PPS, and FAS. The analysis based on the FAS will not take into account the intercurrent events "early discontinuation of treatment due to loss of visits, withdrawal of informed consent, etc., and failure to complete the full-course vaccination". In addition, if the antibody test result is " $<1:10$ ", it is counted as "5". If the antibody test result is " $>1:10240$ ", it is counted as "10241".

(1) Immunogenicity will be compared between the test group and a pooled trivalent control group of two different sizes for H1N1 and H3N2 types, respectively.

✧Analysis of post-vaccination SCR

In the PPS analysis, the 28d post-total vaccination serum HI SCR in all populations, the 28d post-total vaccination serum HI SCR in the susceptible population, and the 28d post-total vaccination serum HI SCR in the non-susceptible population will be calculated in the test group 1, test group 2, and pooled control group under the H1N1 and H3N2 types, respectively, and the two-sided 95%CIs will be calculated using the Clopper-Pearson method. Meanwhile, the Miettinen & Nurminen method will be used to calculate the two-sided 95%CI of the inter-group rate difference, and the Chi-square test/Fisher's exact test will be used for the statistical test of inter-group difference.

In the mFAS and FAS analyses, multiple imputation methods will be used to impute in the missing data in the post-vaccination antibodies, and the 28d post-total vaccination serum HI SCR in all populations, the 28d post-total vaccination serum HI SCR in the susceptible population, and the 28d post-total vaccination serum HI SCR in the non-susceptible population will be calculated for all populations in the test group 1, test group 2, and combined control group under the H1N1 and H3N2 types, respectively based on the imputed datasets. The analysis results of pooled post-imputed datasets will be pooled using Rubin's method to obtain the pooled SCR, the difference in rates between the two groups, and their 95%CIs for each group. If the CI for pooled rate or rate difference is not estimable, the rate or rate difference and its 95%CI will be estimated using the Bootstrap method, which will be sampled 1,000 times with putbacks and seeded = 111.

- ✓ If the lower limit of the two-sided 95%CI for the 28d post-total vaccination serum HI SCR of the test group for this type is $\geq 30\%$, this type has reached the absolute standard for SCR.
- ✓ If the lower limit of the two-sided 95%CI of SCR difference for 28d post-total vaccination serum HI antibody between the two groups (test group 1-pooled control group) and (test group 2-pooled control group) for this type is $\geq -10\%$, the post-vaccination SCR of the test group for this type can be considered to be non-inferior to that of the pooled control group. Otherwise, the non-inferiority test is considered to have failed.

✧ Analysis of post-vaccination antibody SPR

The post-vaccination antibody SPR in all populations, 28d post-total vaccination serum HI SPR in the susceptible population, and the 28d post-total vaccination serum HI SPR in the non-susceptible population, and the 28d post-total vaccination serum HI SPR in the population of <40 before vaccination, and the 28d post-total vaccination serum HI SPR in the population of ≥ 40 before vaccination under the H1N1 and H3N2 types in test group 1, test group 2, and pooled control group will be analyzed using the same statistical methods as those used for post-vaccination SPR.

If the lower limit of the two-sided 95%CI for the 28d post-total vaccination serum HI SPR of the test group for this type is $\geq 60\%$, this type has reached the absolute standard for SPR.

✧ GMT and GMI analysis

In PPS analysis, the covariance analysis model will be employed to analyze the antibodies under H1N1 and H3N2 types, respectively. After logarithmic transformation, the serum HI GMT 28d post-vaccination will be fitted to the covariance analysis model for analysis, with the serum HI GMT 28d post-vaccination after logarithmic transformation as a dependent variable of the model, the logarithmic transformation value of pre-vaccination serum HI antibody GMT as a covariate of the model, and groups will be the fixed effect in the model. The post-vaccination logarithmic transformation value of each group and the least square mean of the difference between groups will be calculated based on the

model. After inverse logarithmic transformation, the post-vaccination antibody corrected geometric mean based on the least square mean of each group, the corrected ratio between groups (test group 1/pooled control group), (test group 2/pooled control group), (test group 1/test group 2), and their 95%CIs will be calculated.

In the mFAS and FAS analyses, the missing data in 28d post-total vaccination serum HI antibody will be imputed using the multiple imputation method, and each imputed dataset will be statistically analyzed using the same covariance analysis model as in the PPS analyses. The analytical results of the imputed datasets will be pooled using Rubin's method and inverse-logarithmically transformed to obtain the corrected GMT for each group, corrected GMT ratio between each pair of groups, and corresponding 95%CIs.

If the lower limit of the two-sided 95%CI for (test group 1/pooled control group) and (test group 2/pooled control group) is $\geq 2/3$, the post-vaccination antibody GMT of the test group for this type is considered to be non-inferior to that of the pooled control group. Otherwise, the non-inferiority test is considered to have failed.

The same method as mentioned above will be adopted to perform a logarithmic transformation on the GMT of serum HI antibody in the susceptible population 28d post-total vaccination, and then fit the covariance analysis model for analysis.

Meanwhile, in the PPS analysis, all population, susceptible population, non-susceptible population, population of <40 before vaccination and population of ≥ 40 before vaccination under the H1N1 and H3N2 types in the test group 1, test group 2, and pooled control group will be statistically described in terms of HI antibody GMT and GMI, respectively, and the group differences will be statistically examined by using the ANOVA with logarithmic transformation. Meanwhile, the 28d post-total vaccination antibody's GMT/GMI ratio and corresponding 95%CIs will be calculated for the two groups, and the inter-group difference will be statistically tested by t-test after logarithmic transformation.

In the mFAS and FAS analyses, the missing data in the post-vaccination antibodies will be imputed using the multiple imputation method, and each imputed dataset will be statistically analyzed using the same method as in the PPS analysis. The analytical results of the imputed datasets will be pooled using Rubin's method and inverse-logarithmically transformed to obtain the GMT for each group, the GMI for each group, the GMT ratio between each pair of groups, the GMI ratio between each pair of groups, as well as their corresponding 95%CIs.

The reverse cumulative distribution plots of antibody titers for H1N1 and H3N2 will be generated separately for test group 1, test group 2, and the pooled control group.

(2) The non-inferiority comparison will be performed for the BV serotype between the test group and the control group

❖ Analysis of post-vaccination SCR

In the PPS analysis, the 28d post-total vaccination serum HI SCR in all populations, the 28d post-total vaccination serum HI SCR in the susceptible population, and the 28d post-total vaccination serum HI SCR in the non-susceptible population will be calculated in test group 1, test group 2, control group 1, and control group 2 under the BV type, respectively, and the two-sided 95%CIs will be calculated using the Clopper-Pearson method. Meanwhile, the Miettinen & Nurminen method will

be used to calculate the two-sided 95%CI of the inter-group rate difference, and the Chi-square test/Fisher's exact test will be used for the statistical test of inter-group difference.

In the mFAS and FAS analyses, multiple imputation methods will be used to impute the missing data in the post-vaccination antibodies, and the 28d post-total vaccination serum HI SCR in all populations, the 28d post-total vaccination serum HI SCR in the susceptible population, and the 28d post-total vaccination serum HI SCR in the non-susceptible population will be calculated for all populations in test group 1, test group 2, control group 1, and control group 2 under the BV type, respectively, based on the imputed datasets. The analysis results of pooled post-imputed datasets will be pooled using Rubin's method to obtain the pooled SCR, the difference in rates between the two groups, and their 95%CIs for each group. If the CI for pooled rate or rate difference is not estimable, the rate or rate difference and its 95%CI will be estimated using the Bootstrap method, which will be sampled 1,000 times with putbacks and seeded = 111.

- ✓ If the lower limit of the two-sided 95%CI for the 28d post-total vaccination serum HI SCR of the test group for this type is $\geq 30\%$, this type has reached the absolute standard for SCR.
- ✓ If the lower limit of the two-sided 95%CI of SCR difference for 28d post-total vaccination serum HI antibody between the two groups (test group 1-control group 1) and (test group 2-control group 1) for this type is $\geq -10\%$, the post-vaccination SCR of the test group for this type can be considered to be non-inferior to that of the control group 1. Otherwise, the non-inferiority test is considered to have failed.

✧ **Analysis of post-vaccination antibody SPR**

The post-vaccination antibody SPR in all populations, 28d post-total vaccination serum HI SPR in the susceptible population, and the 28d post-total vaccination serum HI SPR in the non-susceptible population, and the 28d post-total vaccination serum HI SPR in the population of <40 before vaccination, and the 28d post-total vaccination serum HI SPR in the population of ≥ 40 before vaccination under the H1N1 and H3N2 types in test group 1, test group 2, control group 1 and control group 2 will be analyzed using the same statistical methods as those used for post-vaccination SPR. If the lower limit of the two-sided 95%CI for the 28d post-total vaccination serum HI SPR of the test group for this type is $\geq 60\%$, this type has reached the absolute standard for SPR.

✧ **GMT and GMI analysis**

In PPS analysis, the covariance analysis model will be employed to analyze the antibodies under the BV type in the test group 1, test group 2, control group 1, and control group 2, respectively. After logarithmic transformation, the serum HI GMT 28d post-vaccination will be fitted to the covariance analysis model for analysis, with the serum HI GMT 28d post-vaccination after logarithmic transformation as a dependent variable of the model, the logarithmic transformation value of pre-vaccination serum HI antibody GMT as a covariate of the model, and groups will be the fixed effect in the model. The post-vaccination logarithmic transformation value of each group and the least square mean of the difference between groups will be calculated based on the model. After inverse logarithmic transformation, the post-vaccination antibody corrected geometric mean based on the least square mean of each group, the corrected ratio between groups (test group 1/control group 1), (test group 2/control group 1), (test group 1/control group 2), (test group 2/control group 2) and (test group 1/test group 2) and their 95%CIs will be calculated.

In the mFAS and FAS analyses, the missing data in 28d post-total vaccination serum HI antibody will

be imputed using the multiple imputation method, and each imputed dataset will be statistically analyzed using the same covariance analysis model as in the PPS analyses. The analytical results of the imputed datasets will be pooled using Rubin's method and inverse-logarithmically transformed to obtain the corrected GMT for each group, the corrected GMT ratios between each pair of groups, and corresponding 95% CIs.

If the lower limit of the two-sided 95%CI for (test group 1/control group 1) and (test group 2/control group 1) is $\geq 2/3$, the post-vaccination antibody GMT of the test group for this type is considered to be non-inferior to that of the pooled control group. Otherwise, the non-inferiority test is considered to have failed.

Meanwhile, in the PPS analysis, all population, susceptible population, non-susceptible population, population of <40 before vaccination and population of ≥ 40 before vaccination under the BV type in the test group 1, test group 2, control group 1 and control group 2 will be statistically described in terms of HI antibody GMT and GMI, respectively, and the group differences will be statistically examined by using the ANOVA with logarithmic transformation. Meanwhile, the 28d post-total vaccination antibody's GMT/GMI ratio and corresponding 95% CIs will be calculated for the two groups, and the inter-group difference will be statistically tested by t-test after logarithmic transformation.

In the mFAS and FAS analyses, the missing data in the post-vaccination antibodies will be imputed using the multiple imputation method, and each imputed dataset will be statistically analyzed using the same method as in the PPS analysis. The analytical results of the imputed datasets will be pooled using Rubin's method and inverse-logarithmically transformed to obtain the GMT for each group, the GMI for each group, the GMT ratio between each pair of groups, the GMI ratio between each pair of groups, as well as their corresponding 95% CIs.

The reverse cumulative distribution of antibody titers for BV will be generated separately for test group 1, test group 2, control group 1, and control group 2.

(3) An intergroup comparison of non-inferiority for BY is made between test groups and control groups.

Immunogenicity will be compared between the test group (test group 1 or test group 2) and control group 2 for BY types, respectively, using the same method as for BV types.

Forest plots of the SCR, SPR, and GMT of HI antibody of each serotype in all populations 28d post-total vaccination will be plotted.

Sensitivity Analysis: In mFAS analysis, the missing data in the serum HI antibody and SCR of HI antibody 28d post-total vaccination will be analyzed for sensitivity analysis by using the Tipping Point Analysis (TPA) and the Jump to Reference (J2R) method based on δ adjustment. Evaluate the robustness impact of missing data on the test results. For details, please refer to Section 6.10 on the handling of Missing Data.

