6.10 Handling of Missing Data

In mFAS and FAS set analyses, for missing data in the primary estimand under the assumption of Missing at Random, the Multiple Imputation method will be applied to handle missing data before non-inferiority assessment. The imputation will be performed 10 times, with the random seed set to seed=111222333.

For each imputed complete dataset, the following endpoints will be calculated at 28d post-total vaccination for each serotype:

- SCR
- SPR
- GMT (Geometric Mean Titer)
- GMI (Geometric Mean Increase)

The results from all imputed datasets will then be pooled using Rubin's rules to obtain pooled estimates for SCRs, SPRs, GMTs, and GMIs.

Additionally, for the primary estimand in the mFAS analysis set, sensitivity analyses will be conducted under the assumption of Missing Not at Random to evaluate the robustness of the results.

The following methods will be applied:

- TPA (Tipping Point Analysis) method
- δ -adjusted J2R (Jump to Reference) method

Sensitivity Analysis 1: To evaluate the impact of missing values on the primary estimand, TPA will be used for the sensitivity analysis.

- ✓ For the continuous variable, HI antibody, the TPA method will gradually adjust the possible values of the missing data of HI antibody titers of each serotype after logarithmic conversion, 28d post-total vaccination in each group, to find the critical point that reverses the conclusion of GMT analysis. Among them, the smaller the absolute value of the critical point is, the less impact the missing data has on the trial conclusion, and the better the robustness of the trial conclusion is. The Rubin method will be adopted to combine the analysis results of the datasets after each imputation, and the GMT and its 95% confidence interval of each group, as well as the corrected GMT ratio and its 95% confidence interval between each pair of groups (test group 1 / pooled control group, test group 2 / pooled control group) will be obtained through inverse logarithmic transformation. Among them, the number of seeds for multiple imputation will be taken as seed=111222333, and impute 10 times each time.

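### The bootstrap fallback in SAP 6.8 gives a zero-width or too narrow interval when a subgroup rate is 0% or 100% in every imputed dataset

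*SAP*

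**What the plan says.** SAP section 5 makes the PPS the main immunogenicity population; the mFAS and FAS are complementary. In the PPS, section 6.8 specifies for a single rate that "the two-sided 95%CIs will be calculated using the Clopper-Pearson method", and for a comparison that "the Miettinen & Nurminen method will be used to calculate the two-sided 95%CI of the inter-group rate difference". No fallback is attached to either.

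In the mFAS and FAS, missing post-vaccination titres are multiply imputed (section 6.10: "The imputation will be performed 10 times, with the random seed set to seed=111222333"). Section 6.8 says the results "will be pooled using Rubin's method to obtain the pooled SCR, the difference in rates between the two groups, and their 95%CIs". The fallback follows: "If the CI for pooled rate or rate difference is not estimable, the rate or rate difference and its 95%CI will be estimated". The method named is a bootstrap of 1,000 draws, taken with replacement, with seed 111. It appears under 6.8(1) for H1N1 and H3N2 and again under 6.8(2) for BV; 6.8(3) applies the BV method to BY. The SCR is calculated for all children and for the susceptible and non-susceptible groups.

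For the seroprotection rate (SPR), 6.8 adds strata with pre-vaccination titres below 40 and at 40 or above, and says these "will be analyzed using the same statistical methods as those used for post-vaccination SPR". Read literally, that sentence refers to itself. The SCR paragraph just before it is the sensible referent, but this is an inference.

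Section 6.8 does not say what makes an interval not estimable, which within-imputation variance Rubin's method uses, which type of bootstrap interval is meant, or whether resampling comes before or after imputation.

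**The concern.** A fallback should work in the situation that calls for it. With the usual binomial variance, Rubin's total variance for a rate is zero only when every imputed dataset shows 0%, or every one shows 100%. That is a natural case in which to call the interval not estimable. A bootstrap cannot help there: sampling with replacement from children who all respond yields only responders, so all 1,000 draws agree.

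At stake is the honesty of some intervals in the complementary tables. The PPS table would show a proper interval, and the mFAS or FAS table would show certainty for nearly the same children. The most plausible place is the SPR among children already at 1:40 or more before vaccination. Seroprotection is defined as a titre of 1:40 or more, so these children only have to keep theirs.

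**Working it through.** **Inputs.** From the SAP: 10 imputations, Rubin pooling, 1,000 draws with seed 111, Clopper-Pearson and Miettinen-Nurminen for the PPS, planning rates of 65% (SCR) and 75% (SPR), limits of 30% and 60%, and a margin of -10 points. Assumed: within-imputation variance p(1-p)/n, and all subgroup sizes, since the documents give none.

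**1. The plan's own figures.** The SAP gives no figure for the fallback. The nearest are the sample sizes for the absolute criteria, from n = [1.96(√(p0·q0) + √(p1·q1))/(p1 - p0)]².
- SCR, 65% against 30%: [1.96(0.4583 + 0.4770)/0.35]² = 27.4, so 28, as stated.
- SPR, 75% against 60%: [1.96(0.4899 + 0.4330)/0.15]² = 145.4, so 146, as stated.

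**2. Rubin's variance.** T = W + (1 + 1/10)B, where W is the mean of p(1-p)/n and B is the variance between imputations.
- 60/60 in all 10 sets: W = B = T = 0, so there is no usable interval. The same holds for 0/60.
- 57/60 in all 10 sets: B = 0, but W = 0.95 × 0.05/60 = 0.00079. The interval exists (89.5% to 100.5%).
- Difference, 100% against 90% with 60 per arm: T = 0.9 × 0.1/60 = 0.0015, giving 2.4 to 17.6 points. A difference has T = 0 only if both arms are at a boundary.

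**3. Bootstrap at the boundary.**
- Resampling the imputed sets: 60/60 gave 100% to 100% with standard deviation 0; 0/60 gave 0% to 0%.
- Resampling the incomplete data and then imputing (assumed: 60 children, 3 missing, log10 titre mean 2.3 to 3.0, SD 0.3 to 0.5): from 99.0%-100% to 100%-100%, depending on the setting. This is not always zero width, but it is much narrower than Clopper-Pearson at n = 60.

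**4. The SAP's PPS intervals at the boundary.** For n/n the Clopper-Pearson lower limit is 0.025^(1/n).

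| n/n | Bootstrap of imputed sets | Clopper-Pearson |
|---|---|---|
| 10/10 | 100% to 100% | 69.2% to 100% |
| 20/20 | 100% to 100% | 83.2% to 100% |
| 60/60 | 100% to 100% | 94.0% to 100% |

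With both arms at 100%, the Miettinen-Nurminen limits reduce to -c/(nT + c) and +c/(nC + c), where nT and nC are the test and control sizes, N = nT + nC and c = 1.96² × N/(N - 1). For 20/20 against 10/10, c = 3.8415 × 30/29 = 3.974. The limits are -3.974/23.974 = -16.6 and +3.974/13.974 = +28.4 points; the bootstrap gives 0 to 0. The lower limit is -16.5 points for 20 against 20 and -3.7 for 100 against 50.

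**5. Where a boundary can occur.** At the planning rates with 1,100 children, the chance that all respond is 0.65^1100, about 10^-206 (SCR), or 0.75^1100, about 4 × 10^-138 (SPR). In a stratum of 60 with a true rate of 99% (both assumed) it is 0.99^60 = 0.55.

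**6. When a pass or fail would change.**
- Against 60%: up to n = 7 (Clopper-Pearson lower limit 59.0% at 7, 63.1% at 8).
- Against 30%: up to n = 3 (29.2% at 3, 39.8% at 4).
- Against -10 points with equal arms: up to about 35 per arm (-10.02 points at 35).

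**The case against.** The strongest reply is that the text is under-specified rather than shown to be degenerate. The SAP never ties the fallback to 0% or 100%. A team might also call an interval not estimable when the between-imputation variance is zero, because Rubin's degrees of freedom divide by it. The rate can then be well inside the range, as with 57/60, and the bootstrap works. Nor does the SAP fix the order of resampling and imputation. Both points stand. They limit the claim to one likely trigger, with zero width certain only if the imputed sets themselves are resampled.

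The reach into the SPR strata is also open to question. It depends on reading the SPR sentence as pointing to the SCR methods. Section 6.10 ties imputation to the primary estimand and ends by leaving missing data in other immunogenicity endpoints unprocessed, so it is unclear whether the stratum at 1:40 or more is imputed at all. That also stands. The SCR subgroups are covered explicitly in 6.8, but nothing in the documents suggests that all, or none, of the non-susceptible children will show a four-fold rise.

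Finally, no main conclusion depends on these cells. The primary analysis is in the PPS. Protocol 7.2 sets its criteria for the total population and extends them to the susceptible group; it sets none for the non-susceptible group or the stratum at 1:40 or more. This is why the point is minor.

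**Conclusion.** The point holds as a minor correction to complementary tables. If every imputed dataset is at the same boundary, and for a difference both arms are at one, bootstrapping those datasets gives a zero-width interval. Resampling before imputing can still give one that is too narrow. This rests on a p(1-p)/n variance, on zero variance counting as not estimable, and, for the SPR, on reading the self-reference as the SCR methods. The interval sizes shown are illustrations at assumed subgroup sizes.

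A reader might infer three stronger things that the documents do not support:
- That the fallback always fails when used. The trigger is undefined, and away from a boundary the bootstrap is not degenerate.
- That the primary analysis or the total-population criteria are at risk. The PPS does not use the fallback, and a boundary in the total population is impossible in practice at the planning rates.
- That the same fallback in the section 6.10 sensitivity analyses must change. Those analyses address the primary estimand in the mFAS, that is, the total population. The jump-to-reference step also draws missing SCR outcomes at 10 points below the control rate, which moves results away from 100%.

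**What to change.** Amend the fallback in 6.8 only:

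- When every imputed dataset has a rate at the same boundary (0% or 100%), report the Clopper-Pearson interval on the completed data. When both arms of a comparison are at a boundary, report the Miettinen-Nurminen interval for the difference. Stratum membership depends on the baseline titre, which the mFAS and FAS require, so all 10 datasets then have the same counts and nothing needs pooling. Add a note that this treats imputed values as observed.
- Define not estimable. Keep the bootstrap for any other such case, stating its resampling unit and whether resampling precedes imputation.
- Make the SPR sentence refer to the SCR methods, if that is what is meant.

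Section 6.10 needs no change. The cost is SAP wording; both intervals are already required for the PPS tables.
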